5.2.3 Concomitant medication date imputation

Rules for imputing the CM end date (including on-going records):

- If imputing end dates, this should be done prior to calculating imputed start dates.
- When the medication is ongoing at the end of the study, no numeric end date is derived.
- If the end date is completely missing no numeric end date is derived.
 - a. If CM end day is missing and CM month/year are non-missing, then impute CM date as the minimum of study end date and the last day of the month.
 - b. If CM end day/month are missing and CM year is non-missing, then impute CM date as the minimum of study end date and the end of the year (31DECYYYY).

c. If imputed CM end date is less than the complete CM start date, use the complete CM start date as the imputed CM end date.

Rules for imputing the CM start date:

- If imputing end dates, then this should be done prior to calculating imputed start dates.

The following table explains the notation used in the logic matrix.

	Day	Month	Year
Partial CM Start Date	Not used	MON	YYYY
Treatment Start Date	Not used	TRTM	TRTY

The following matrix explains the logic behind the imputation.

	MON MISSING	MON < TRTM	MON = TRTM	MON > TRTM
YYYY MISSING	(a) Uncertain	(a) Uncertain	(a) Uncertain	(a) Uncertain
YYYY < TRTY	(a) Before Treatment Start	(a) Before Treatment Start	(a) Before Treatment Start	(a) Before Treatment Start
YYYY = TRTY	(a) Uncertain	(b) Before Treatment Start	(a) Uncertain	(c) After Treatment Start
YYYY > TRTY	(a) After Treatment Start	(b) After Treatment Start	(b) After Treatment Start	(b) After Treatment Start

1. If the CM start date year value is missing, then the imputed CM start date is set to one day prior to *Treatment start date (TR01SDT)*.
2. If the CM start date year value is less than the *Treatment start date (TR01SDT)* year value, then the CM started before treatment. Therefore;
 - a. If the CM month is missing, then the imputed CM start date is set to the mid-year point (01JulYYYY).
 - b. Else if the CM month is not missing, then the imputed CM start date is set to the mid-month point (15MONYYYY).
1. If the CM start date year value is greater than the *Treatment start date (TR01SDT)* year value, the CM started after treatment. Therefore;
 - a. If the CM month is missing, then the imputed CM start date is set to the year start point (01JanYYYY).
 - b. Else if the CM month is not missing, then the imputed CM start date is set to the month start point (01MONYYYY).
1. If the CM start date year value is equal to the *Treatment start date (TR01SDT)* year value;
 - a. And the CM month is missing or the CM month is equal to the *Treatment start date (TR01SDT)* month, then the imputed CM start date is set to one day prior *Treatment start date (TR01SDT)*.

- b. Else if the CM month is less than the *Treatment start date (TR01SDT)* month, then the imputed CM start date is set to the mid-month point (15MONYYYY).
- c. Else if the CM month is greater than the *Treatment start date (TR01SDT)* month, then the imputed CM start date is set to the month start point (01MONYYYY).

If complete (imputed) CM end date is available and the imputed CM start date is greater than the complete (imputed) CM end date, then imputed CM start date should be set to the complete (imputed) CM end date.

If there is no end date and ongoing check is not ticked, the CM will be considered as ongoing and included in the summary table.

5.2.3.1 Prior therapies date imputation

All therapies on the Prior urticaria therapy CRF page will be considered as prior. No additional imputation will be performed.

5.2.3.2 Post therapies date imputation

Not applicable.

5.2.3.3 Other imputations

Not applicable.

5.3 AEs coding/grading

AEs will be coded using the MedDRA version at the database lock.

AE grading is not applied in this study.

5.4 Clinically notable criteria and abnormalities

5.4.1 Clinically notable criteria

The following notable criteria will be used in the study

Laboratory value

Variable	Notable criterion
Creatinine (umol/L), Plasma/Serum	>ULN – 1.5 x ULN >1.5 - 3.0 x ULN; >1.5 - 3.0 x baseline >3.0 - 6.0 x ULN; >3.0 x baseline
Blood urea nitrogen* (mmol/L)	1.25 – 2.5 x ULN >2.5 – 5.0 x ULN >5.0 – 10.0 x ULN >10.0 x ULN
Albumin (g/L)	<LLN - 30 g/L <30 - 20 g/L <20 g/L

Alanine aminotransferase, ALT (U/L)	Normal baseline >ULN - 3.0 x ULN >3.0 – 5.0 x ULN >5.0 – 20.0 x ULN >20.0 x ULN	Baseline abnormal 1.5 – 3.0 x baseline >3.0 – 5.0 x baseline >5.0 – 20.0 x baseline >20.0 x baseline
Aspartate aminotransferase, AST (U/L)	Normal baseline >ULN - 3.0 x ULN >3.0 – 5.0 x ULN >5.0 – 20.0 x ULN >20.0 x ULN	Baseline abnormal 1.5 – 3.0 x baseline >3.0 – 5.0 x baseline >5.0 – 20.0 x baseline >20.0 x baseline
Alkaline phosphatase, ALP (U/L)	Normal baseline >ULN – 2.5 x ULN >2.5 – 5.0 x ULN >5.0 – 20.0 x ULN >20.0 x ULN	Baseline abnormal 2.0 – 2.5 x baseline >2.5 – 5.0 x baseline >5.0 – 20.0 x baseline >20.0 x baseline
Gamma glutamyl transferase, GGT (U/L)	Normal baseline >ULN – 2.5 x ULN >2.5 – 5.0 x ULN >5.0 – 20.0 x ULN >20.0 x ULN	Baseline abnormal 2.0 – 2.5 x baseline >2.5 – 5.0 x baseline >5.0 – 20.0 x baseline >20.0 x baseline
Bilirubin (umol/L)	Normal baseline >ULN – 1.5 x ULN >1.5 – 3.0 x ULN >3.0 – 10.0 x ULN >10.0 x ULN	Baseline abnormal >1.0 – 1.5 x baseline >1.5 – 3.0 x baseline >3.0 – 10.0 x baseline >10.0 x baseline
Platelets (10E9/L), Blood	<LLN # to 75 x10E9/L <75 - 50 x10E9/L < 50- 25 x10E9/L < 25 x10E9/L	
Leukocytes, WBC (10E9/L)	<LLN - 3.0 x 10E9/L <3.0 - 2.0 x 10E9/L <2.0 - 1.0 x 10E9/L <1.0 x 10E9/L >100 x 10E9/L (leukocytosis, grade 3)	
Hemoglobin (g/L)	<LLN - 100 g/L <100 - 80g/L <80 g/L	
Lymphocytes (10E9/L)	<LLN - 0.8 x 10E9/L <0.8 - 0.5 x 10E9/L <0.5 - 0.2 x 10E9/L <0.2 x 10E9/L >4.0 - 20 x 10E9/L (grade 2 lymphocytosis) >20 x 10E9/L (grade 3 lymphocytosis)	
Neutrophils (10E9/L)	<LLN - 1.5 x10E9/L <1.5 - 1.0 x 10E9/L <1.0 - 0.5 x 10E9/L	

	<0.5 x 10E9/L
# LLN = 140 x10E9/L	
* No CTCAE grades provided for BUN. Values derived from Division of Microbiology and Infectious Diseases (DMID) grading system	
When the parameters have different criteria for different baseline status (e.g., ATL, AST), the patients with normal baseline will follow the criteria on the left side, and the patients with abnormal baseline will follow the criteria on the right side.	

Vital sign

- Heart rate < 60 beats per minute (bpm) (bradycardia)
- Heart rate > 100 beats per minute (bpm) (tachycardia)
- Systolic blood pressure < 90 and \geq 140 mmHg (hypertension)
- Diastolic blood pressure of < 60 and \geq 90 mmHg (hypotension)

ECG

- QT interval - >500 msec
- QTcF (Fridericia's) interval - males > 450 msec
- QTcF (Fridericia's) interval - females > 460 msec
- QTcF change from baseline >30 msec, >60 msec
- PR >250 msec

5.4.2 Abnormalities**Liver-enzyme abnormalities****Table 5-1 Liver-enzyme abnormalities**

Parameter	Notable criterion
ALT	>3xULN; >5xULN; >10xULN; >20xULN
ALT or AST	>3xULN; >5xULN; >8 xULN;>10xULN; >20xULN
(ALT or AST) & TBL	>3xULN & (TBL >1.5xULN; >2xULN)
TBL	1 xULN; 1.5xULN ; >2xULN
ALP	1.5xULN ; >2xULN; >5xULN
ALP & TBL	> 3xULN; > 5xULN; & (TBL 2xULN;)
(ALT or AST) & TBL & ALP	ALT or AST>3xULN & (TBL)>2xULN & ALP≤2xULN (potential Hy's Law case)

AST = Aspartate aminotransferase; also known as SGOT, ALT = Alanine aminotransferase; also known as SGPT, ALP = Alkaline phosphatase, TBL = Total bilirubin

Renal abnormalities**Table 5-2 Renal abnormalities**

Parameter	Notable criterion
Serum creatinine	Increase 25% – 49%
Serum creatinine	Increase \geq 50% +

Parameter	Notable criterion
New onset dipstick proteinuria	≥1+

5.5 Statistical models

5.5.1 Primary analysis

Not applicable.

5.5.2 Key Secondary analysis

Mixed model with repeated measures (MMRM):

The supportive analyses for UAS7, HSS7 and ISS7 will be performed.

The SAS procedure proc mixed will be used for this analysis with the following code:

```
proc mixed data=..... order=internal covtest;  
class subject week cuind;  
model change = baseline week cuind baseline*week / s ddfm=kr;  
repeated week / type=un subject=subject;  
lsmeans week / cl e OM;  
ods output LSmeans=mean ConvergenceStatus=convtest;  
run;
```

where change = change from baseline UAS7 score

baseline = baseline UAS7 score

week = study week

[REDACTED] [REDACTED]

subject = subject

If the computation of the MMRM model takes extreme amount of time, the ddfm=bw option could be considered. If the model with an unstructured covariance matrix does not converge, SAS will give a warning as “Unable to make hessian positive definite” or “Unable to Converge” or “stopped because of infinite likelihood”. Meanwhile, the Status variable in the convtest dataset created will take on the value 0 or 1. In this case, the compound-symmetry structure should be used, by replacing type=un in the above codes with type=cs.

If after this step the model still does not converge, remove the covariates in the following order until it converges: baseline*week, [REDACTED]

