1.1 Study design

This is a Phase III multi-center, open-label, single arm study. The study consists of 3 distinct periods:

- Screening period (Day -28 to Day -14): Duration of up to 4 weeks in which subjects who have given informed consent are assessed for eligibility.
- Treatment period (52 weeks): The subjects will be seen in the clinic every 4 weeks.
- Post-treatment follow-up period (12 weeks): This period consists of a subject visit in the clinic every 4 weeks with the final visit (Visit 1999) occurring 16 weeks after the last treatment dose.

Figure 1-1 Study design

This study is designed to obtain safety data of QGE031 in 65 Japanese CSU patients. Details of sample size are described in [Section 3](#) in this document.

The study population will consist of approximately 65 male and female subjects aged ≥ 18 years who have been diagnosed with CSU and who remain symptomatic despite the use of H1-AH.

It is anticipated that approximately 81 subjects will need to be screened (an estimated screening failure rate of 20%) in order to enroll approximately 65 subjects into the 52 week treatment period (see [Figure 1-1](#)).

No randomization is planned in this study.

The primary objective of this study is to investigate the safety and tolerability of ligelizumab 120 mg q4w for 12 months.

The primary variable is the number and percentage of patients who reported treatment emergent adverse events during the 64 week (treatment period+ follow-up period) study period.

No interim analysis is planned in this study.

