2.6.2 Statistical hypothesis, model, and method of analysis

No formal statistical analysis will be provided.

Summary tables will be presented by visit or week using descriptive statistics. Categorical variables will be presented as frequencies and percentages. For continuous variables, mean, standard deviation, median, minimum, and maximum will be presented. Mean the change from baseline (UAS7, HSS7, ISS7 and DLQI) will be shown descriptively with 95% confidence interval based on one-sample t-test. Proportion of subjects ($UAS7=0$, $HSS7=0$, $ISS7=0$ and $DLQI=0/1$) will also be shown with 95% confidence interval based on the Clopper-Pearson (exact) method. All analyses will be provided descriptively and no formal statistical testing will be applied. Figures will also be provided. The $UAS7=0$ response status will be defined based on the weekly UAS7 score by week. For instance, if the observed $UAS7=0$ at week 12, it will be considered as response, otherwise it is considered as a non-response unless UAS7 is missing. No non-responder imputation is planned in this study.

For time to achievement of complete UAS7 response, Kaplan-Meier estimator will be used to estimate the cumulative incidence function and the results will be plotted. Only the treatment period will be included in this time to first response analysis. Time to first complete $UAS7 = 0$ response achievement will be considered censored at the date of the last non-missing weekly score for any patient who is a non-responder. For the time to achievement of $UAS7 \leq 6$ response analysis, the patients with baseline $UAS7 \leq 6$ response will be excluded from the analysis as well.

For subjects who completed 52 week treatment period, time to loss of complete UAS7 response from Week 52 will be analyzed using Kaplan-Meier estimator similarly as the time to achievement of complete UAS7 response analysis. Time to first loss of complete UAS7 response from Week 52 for patients having achieved complete $UAS7=0$ response at Week 52 will be considered censored at the date of the last non-missing weekly score for any patient who remains as a responder. Time to loss of response analyses will be based on post-treatment follow-up period.

Time to $UAS7 \geq 16$ for patients having achieved $UAS7 \leq 6$ at week 52 will be performed in a similar way as the time to loss of complete UAS7 response analysis.

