2.6.4 Supportive analyses

In order to mitigate the impact of missing data of UPDD (HSS, ISS), model based approach will be applied if applicable. A linear mixed model with repeated measures (MMRM) will be used to estimate treatment differences for change from baseline in UAS7 score up to the end of study, based on the SAF. The MMRM model will include [REDACTED], visit week, baseline UAS7 score and interaction of baseline UAS7 score by visit week as fixed effects. Repeated measures within subject are modeled using an unstructured covariance of the error terms. If the model does not converge, the compound symmetry covariance structure will be used. For details, please see the Appendix.

For HSS7 and ISS7, same analyses will be performed.

[REDACTED]
The SAS program code and is described in section 5.5.2.

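### The supportive single-arm MMRM takes its weekly LS means at the observed mean baseline, so its 95% limits are too narrow if read as limits for the mean change from baseline

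*SAP*

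**What the plan says.** SAP 1.1 describes the design: "This is a Phase III multi-center, open-label, single arm study". For UAS7, HSS7, ISS7 and DLQI, SAP 2.6.2 states that the mean change from baseline "will be shown descriptively with 95% confidence interval based on one-sample t-test".

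SAP 2.6.4 adds a supportive model with this purpose: "In order to mitigate the impact of missing data of UPDD (HSS, ISS), model based approach will be applied if applicable". It says the model "will be used to estimate treatment differences for change from baseline in UAS7 score up to the end of study, based on the SAF" and lists among its terms "baseline UAS7 score and interaction of baseline UAS7 score by visit week as fixed effects". HSS7 and ISS7 are to be analysed in the same way.

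SAP 5.5.2 gives the code. The mean model is "model change = baseline week cuind baseline*week / s ddfm=kr", the covariance is "repeated week / type=un subject=subject", and the output is "lsmeans week / cl e OM". Compound symmetry replaces the unstructured matrix if the fit does not converge. No treatment term, variance correction or statement that the limits are conditional on baseline accompanies the code.

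**The concern.** With two randomised arms, adjusting for baseline gives a real gain in precision, because the baseline term cancels in the treatment contrast. Here there is one arm and nothing cancels. The LS mean for a week is the fitted change at the observed mean baseline, and its standard error takes that mean as a fixed number. The limits are therefore correct for patients whose baseline equals this sample's mean. They are too narrow for the mean change in the population.

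With complete data the LS mean equals the raw mean change, so a report would show the same point estimate twice: once with the t interval and once with a tighter model-based interval. A reader could credit the tighter limits to the missing-data model when they only reflect a narrower question. The reference in 2.6.4 to treatment differences adds to this, since the design contains no such contrast.

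**Working it through.** **Inputs from the documents.** N = 58 with data, SD of change 13, mean change -22.0 (SAP 3.2); baseline UAS7 of at least 16 on a 0–42 scale (protocol 5.1). The code sets no confidence level, so the usual 95% applies.

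**Assumed inputs.** Baseline SD s0 and slope b_t are not in the documents. I take s0 from 6 to 7.5 and b_t from -0.6 to -1. A uniform spread over 16–42 gives s0 = 26/√12 = 7.5.

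**The plan's own figure.** 1.96 × 13/√58 = 3.35, interval (-25.35, -18.65). This agrees with the stated 3.3 and (-25.3, -18.7). The t version gives 3.42. Both use the full SD of change, baseline variation included.

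**Variance.** For week t:

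- Var(mean change) = [residual variance + b_t²·s0²]/N
- squared LS-mean standard error = residual variance/N
- width ratio = √(1 − b_t²·s0²/169)
- approximate non-coverage = 2·[1 − Φ(1.96 × ratio)]

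| s0 | slope | b_t²·s0² | width ratio | half-width (3.35 × ratio) | non-coverage | widening needed (1/ratio − 1) |
|---|---|---|---|---|---|---|
| 6 | -0.6 | 12.96 | 0.961 | 3.21 | 6.0% | 4% |
| 7 | -0.7 | 24.01 | 0.926 | 3.10 | 7.0% | 8% |
| 6 | -1.0 | 36.00 | 0.887 | 2.97 | 8.2% | 13% |
| 7.5 | -1.0 | 56.25 | 0.817 | 2.73 | 10.9% | 22% |

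Simulation at N = 58 agrees: 10.7% at slope -1 and s0 = 7.5, against about 5% for the t interval. Adding b_t²·s0²/N back restores about 5%.

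**High response.** Simulated coverage with s0 about 6.3 and non-responders' scores proportional to baseline:

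| Share with UAS7=0 | Model-based coverage | Width relative to t interval |
|---|---|---|
| 40% | 92.4% | 0.91 |
| 60% | 90.8% | 0.87 |
| 80% | 85.7% | 0.77 |
| 90% | 76.8% | 0.62 |

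The t interval stayed at 94–95%. In the limit where every patient reaches 0, change equals minus baseline, the residual variance is zero and the model-based interval has no width. These response shares are illustrations; the documents do not predict them.

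**Possible repair with baseline as a week-0 response.** This is sound with an unstructured matrix. Under the compound-symmetry fallback it forces baseline to share the variance and correlation of the on-treatment weeks. With 16 visits and an assumed inter-week correlation of 0.7, non-coverage was 16.2% against 10.1% for the current code at slope -1, and 13.0% against 6.3% at slope -0.6. At correlation 0.5 the two were about equal. The fallback is a live possibility: 16 visits need 16·17/2 = 136 covariance parameters, and all 64 study weeks would need 64·65/2 = 2,080, from about 65 patients.

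All these simulations used complete data and left out cuind.

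**The case against.** The strongest reply is that little depends on this model. The primary endpoint is safety, SAP 2.6.2 rules out formal testing, and the main efficacy interval is the t interval, which is right. The MMRM is supportive and to be used if applicable. The SAP does not say that its limits target the unconditional mean, and at the observed mean baseline they are valid. All of that stands and limits the weight of the point. It does not remove it, because the limits would appear unlabelled beside t intervals for mean change.

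The reply on size also stands in part. The loss depends on two quantities the documents do not give, and near the planning SD it is modest. A reader might infer error rates of 20% to 35%. Those arise with slope -1, s0 = 7.5 and a post-baseline SD of 6 or 4, which imply an SD of change of √(56.25 + 36) = 9.6 or √(56.25 + 16) = 8.5. The plan assumes 13. A reader might also infer that the shortfall always grows with efficacy. It is not strictly monotone: when post-treatment scores do not depend on baseline, coverage at low response rates can rise slightly before it falls.

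Finally, a reader might take this model to be the only handling of missing diary data. SAP 2.6.3 fills a missing half-day from the other entry and prorates weeks with at least 4 daily scores. The MMRM is the only visible model-based handling of weekly scores that are wholly missing.

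**Conclusion.** The point holds for the supportive MMRM limits when they are read as limits for the mean change from baseline. With N = 58, SD 13, assumed baseline SD 6 to 7.5 and slope -0.6 to -1, non-coverage is about 6% to 11% instead of 5%. It is larger if most patients reach UAS7=0. The same mechanism applies to HSS7 and ISS7, for which I have not put numbers.

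The documents do not support the stronger conclusion that the trial's efficacy intervals are unreliable. The one-sample t intervals already include baseline variation, and neither they nor the primary safety endpoint is affected. The correction is worth making before analysis because it is cheap and the tighter limits would otherwise be easy to misread.

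**What to change.** In SAP 2.6.4 and 5.5.2:

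1. Keep the prespecified model, including cuind. Compute the LS-mean limits either by adding b_t²·s0²/N to each squared standard error or by a bootstrap that resamples whole subjects, baseline together with outcomes. State that this applies under both the unstructured and the compound-symmetry fits. The add-back restores the baseline term only and was checked on complete data; the bootstrap also carries the sampling of cuind and the missing-data pattern.
2. Use a model with baseline as the week-0 response only with an unstructured covariance, never under the compound-symmetry fallback.
3. Replace the treatment-difference wording in 2.6.4 with estimation of the within-group mean change from baseline by week.
4. Apply the same changes to HSS7 and ISS7.

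The cost is a few lines of SAP text and code and no new data. The supportive intervals widen by about 4% to 22% over the assumed range, and by more if response is very high.
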